### 3.1 Overview of Recruitment and Screening

The final number of participants will be 89 men and women (9 for Phase I, 80 for Phase II).

If an individual decides not to participate at any point during the recruitment and/or screening process, the reason(s) for non-interest should be documented in the appropriate tracking log.

[PHASE II ONLY] Participants will be randomized after the baseline interview or within one week of the baseline interview if the randomization criteria are unclear. Participants who are randomized but who fail to begin treatment at SWNARC or through MICRA will not be replaced. Participants must begin treatment at SWNARC or MICRA within two weeks after randomization.

A flow chart of the screening process appears below:

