### **3.5 Transitioning to the Baseline Assessment**

If an individual is eligible for and interested in the study and signs the consent form, the next step is to continue with the baseline interview. In some cases, the RA will have time to continue with the baseline interview immediately following the screening and consent. This will depend on the RA and participant's availability and energy levels. If the participant does not continue with the baseline interview, then the RA will schedule another time to complete the baseline interview. The scheduled baseline interview date will be recorded in the Participant Enrollment Log. The baseline interview must be completed within two weeks of the screening, and the RA should call to remind the participant about the baseline interview the day before it is scheduled. The RA will say something along these lines: "Okay [insert name], now we need to schedule your first research appointment. It would be best if we could schedule it for tomorrow, but if that doesn't work for you we need to schedule it within the next week. The next visit will last approximately three to four hours. You will meet with me to fill out some paper questionnaires and complete a short interview." If the participant misses three scheduled baseline interview appointments, they will be referred back to SWNARC for treatment there. Only individuals who complete the baseline interview (and are randomized if in

Phase II) will count towards the total number of study participants. Participants who are randomized but do not begin treatment will still be invited to continue on with the research assessments.

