**4.2 Biological Assessments**

**4.2.1 Breath Alcohol Content**

If the participant completes his or her screening on the same day as the baseline assessment, then the BAC does not have to be repeated. This should be noted on the Baseline Checklist. If the baseline assessment is on a separate day, then the participant must be given a BAC before completing the assessment. The results of the BAC are recorded on the baseline checklist. If the BAC is less than or equal to .05, continue on to the oral fluid screen. If the BAC is > .05, the RA will inform the individual of his or her BAC level and that it is not safe to drive. The RA will inquire about the individual's transportation to and from the screening. The RA may call someone to pick up the participant, or let him or her stay in the office until his or her BAC is less than or equal to .02. If the person insists on driving away, the RA will inform them that they have to call the police but will not try to restrain him or her from leaving the building. If BAC > .05, the individual must reschedule the baseline assessment for another day. Even if an

individual has a BAC of .05 or lower, the RA has the right to not continue with the assessment if the individual smells like alcohol or seems intoxicated or impaired by other drugs. It is important to be safe. In such cases, the RA will ask the person to reschedule for another day.

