#### **4.5 Ending the Baseline Assessment**

When all assessment instruments have been completed, the RA will provide the participant with a \$50 gift certificate to Halona Plaza (see Incentives SOP for details). The RA will enter the completed baseline assessment date into the Participant Enrollment log, record the estimated 4-month follow-up date, and provide the participant with an appointment card for the 4-month follow-up. Follow-up appointments should be scheduled approximately 2 weeks before the estimated 4-month follow-up date.

In Phase II, the RA will open the randomization envelope (see Chapter 5 for details) and inform the participant of their treatment assignment. For those assigned to SWNARC, the RA will inform the participant that his or her referral packet will be sent to SWNARC, and that SWNARC will call to schedule a date and time for the participant to go to SWNARC and complete the intake process. For Phase II participants assigned to MICRA and all Phase I participants, the RA will walk them over to a counselor's office and have them schedule the first treatment session. If all counselors are occupied, the RA will schedule an appointment for the participant with a counselor.

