## **Chapter 5: Randomization (Phase II Only)**

### **5.1 Introduction to Randomization**

Randomization only applies to Phase II participants; all Phase I participants will receive MICRA. Randomization divides the study participants equally between two groups using a chance process that guards against the possibility that a certain type of participant (e.g., those with more severe substance use) ends up in one study condition more often than in another. Participants will be randomized upon completion of the baseline interview. Eighty individuals will be randomized (40 per treatment condition). No provisions have been made for replacement of participants that do not adhere to the protocol once treatment intervention has been assigned, although research interviews with these participants will continue to determine how they are doing at the follow-up interviews.

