### **5.2 The Randomization Process**

Once participants have completed all baseline assessments, the RA will determine the treatment assignment by pulling out the envelope with the appropriate number. Sixty cards have been numbered with 30 “Ms” and 30 “Zs” (M = MICRA; Z = SWNARC), placed in individual envelopes, and shuffled thoroughly. The envelopes are numbered sequentially from one to 60. The first person that consents and completes the baseline will receive the treatment assignment from envelope 1, the second individual will receive the assignment from envelope 2, and so on. The treatment assignment will be recorded on the Baseline Checklist. The envelopes will be shuffled by the PI, Co-PI, and RA before Phase II begins. A second randomization process will occur to accommodate the increase in recruitment (from 60 to 80) that was approved by the National Institute of Drug Abuse (funding agency) in March of 2012. Ten additional cards will be labeled with “MICRA” and ten will be labeled as “SWNARC.” These cards will be placed in envelopes and shuffled, and the envelopes then will be labeled from 61 to 80. Similar to the process described above, the 61st through 80th participants will receive the treatment assignments listed on the cards in the envelopes corresponding to numbers 61 through 80.

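### The RA who makes the last eligibility check, takes consent and times the baseline also pulls and opens the allocation envelopes, and no stated safeguard stops the next assignment being read early

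*Protocol*

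**What the plan says.** **Allocation.** Protocol 5.2 states that "the RA will determine the treatment assignment by pulling out the envelope with the appropriate number". Section 4.5 adds that "the RA will open the randomization envelope (see Chapter 5 for details) and inform the participant of their treatment assignment". The first person to consent and finish the baseline gets envelope 1, the next gets envelope 2, and so on.

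**Preparation.** For the first set, "The envelopes will be shuffled by the PI, Co-PI, and RA before Phase II begins". For the added set, "These cards will be placed in envelopes and shuffled, and the envelopes then will be labeled from 61 to 80"; no one is named to do this. Chapter 5 does not say that the envelopes are sealed or opaque, where they are kept or who holds them. It cites no separate randomization procedure.

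**Enrolment and timing.** The same RA re-checks the basic criteria (3.4.3), gives the diagnostic interview (3.4.4) and takes consent (3.4.7). On timing, "If the participant does not continue with the baseline interview, then the RA will schedule another time to complete the baseline interview" (3.5), and the RA may split the baseline over two days (4.1). Even with an acceptable breath reading, "the RA has the right to not continue with the assessment if the individual smells like alcohol or seems intoxicated" (4.2.1).

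**When randomization happens.** Section 5.1: "Participants will be randomized upon completion of the baseline interview". Section 3.1 also allows it "within one week of the baseline interview if the randomization criteria are unclear". Section 5.2 contains no criteria of that kind.

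**What candidates are told.** In the Phase II script (Appendix C) the RA says that she will not know the arm.

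**The concern.** Shuffled envelopes give a random sequence. Concealment is a separate requirement: whoever decides when a person enters must not be able to learn the next assignment first. Here the order of finishing the baseline fixes the envelope, the RA has discretion over when a baseline is finished, and the same RA handles the envelopes. Without stated sealing or outside custody, the RA could look at the next card and then bring forward or defer a pending candidate. The statement in the Appendix C script is not secured by any written procedure.

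If that happened, people with better or worse prognosis could be steered to one arm, which is what 5.1 says randomization is there to prevent. It would bias the effect sizes that the pilot exists to estimate (Aim 4 in 1.1). The baseline covariates in 7.5 would remove the part of the shift that those measures carry, but not imbalance in unmeasured prognosis.

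**Working it through.** **1. The plan's own counts.** 30 + 30 = 60 and 10 + 10 = 20, so 80 in all and 30 + 10 = 40 per arm, as 5.1 states. No sample size is in dispute.

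**2. Do the stated safeguards block early reading?**
- Recovery center staff approach people first and apply the basic exclusions (3.3). This narrows who reaches the RA, not the order in which they finish the baseline.
- The supervisor or principal investigator reviews unclear cases (3.4.5, 3.4.7), but only when the RA is unsure.
- Screening is once only (2.3) and three missed baselines end entry (3.5). There are limits of five business days (3.3), two weeks (3.5) and one week for a split baseline (4.1). These bound deferral but leave room for it.
- Sequential numbering and opening after the baseline fix which envelope applies, not whether it was seen beforehand.
- The logs in 5.4 list no envelope number or opening time, and the monthly check in 7.1.4 reviews form completion. Both may reveal misuse afterwards.

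None of them prevents early reading.

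**3. How large could the bias be?** The protocol gives no input for this, so every input below is assumed. Envelopes 1 to 60 are treated as neutral.

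*Closed form.* Let v be the shift, in SD of prognosis, of each entrant toward the arm that the RA has in mind.
- All of 61 to 80 read early: 10 of 40 in one arm move by +v and 10 of 40 in the other by −v. Bias = 2 × (10/40) × v = 0.5v. For v = 0.1, 0.25 and 0.5 this is 0.05, 0.125 and 0.25 SD.
- Counting past assignments only, with the 10/10 split known: excess correct guesses = 2^19 / C(20,10) − 1/2 = 2.34. Bias = 2 × 2.34 × v / 40 = 0.117v, or 0.012 to 0.058 SD for v = 0.1 to 0.5.
- Difference that concealment would close: 0.5v − 0.117v = 0.383v.

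*Reordering only.* Simulation with 20,000 runs per cell. At most two candidates are pending. The RA takes the better or worse of the two to suit the known next arm, and nobody is passed over more than twice. Here p is the share of entries with a second candidate pending, and r is the correlation between what the RA sees and true prognosis.

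| r | p | Simulated bias (SD) | 0.5 × p × r × 0.564 |
|---|---|---|---|
| 0.5 | 25% | 0.034 | 0.035 |
| 0.5 | 50% | 0.066 | 0.071 |
| 1.0 | 25% | 0.072 | 0.071 |
| 1.0 | 50% | 0.134 | 0.141 |

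The last column is a hand check. The expected larger of two standard normal values is 1/√π = 0.564, so v ≈ p × r × 0.564 if each pair is fresh. It agrees closely. The equivalent v is twice the bias, 0.07 to 0.27. Counting past assignments under the same rules gives 0.001 to 0.006 SD.

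*After baseline adjustment.* If the covariates carry an assumed 25% to 75% of the shift, what is left runs from 0.034 × 0.25 = 0.009 to 0.134 × 0.75 = 0.10 SD.

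*For scale.* Unadjusted 95% half-width at 40 per arm = 1.96 × √(2/40) = 0.438 SD.

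**4. Does the one-week allowance reorder entry?** Section 5.2 ties the envelope to the order of consent and baseline completion, and 4.5 has the completed baseline date logged. Holding back the draw leaves that person's envelope number unchanged. What the allowance does leave open is ruling someone out after the baseline on criteria that the protocol does not define.

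**The case against.** The point rests on silence. Opening an envelope implies that it was closed, and no text says that the cards are accessible beforehand. A few pages, most of them in the appendices, were not available for this check, so a sealing statement there cannot be excluded. This stands in part: if the envelopes are in fact sealed and locked away, a sentence saying so settles that half. Chapter 5 is nonetheless the designated place and is silent, and the enroller would still handle the sequence.

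The bias sizes have no source in the protocol. That also stands; they show scale only.

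Three stronger readings are tempting, and the documents do not support them.
- *The RA's part in the shuffling exposes the sequence.* The cards are already in envelopes and three people shuffle them. That is not a defect in itself.
- *The one-week allowance in 3.1 is a second way to steer people to an arm.* The numbering rule in 5.2 rules this out, and a draw out of order would show against the logged baseline dates.
- *The RA alone controls who enters.* Intake staff filter first and unclear cases go to the principal investigator. What the RA holds is the last routine check, consent and the timing.

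**Conclusion.** The concern holds as a gap in allocation concealment: the person who times entry also holds and opens the next assignment, and nothing stated prevents early reading. It does not show that any envelope was read or any participant steered.

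The likely size is modest. Reordering within 61 to 80 gives about 0.03 to 0.13 SD, or 0.01 to 0.10 SD after adjustment, if a second candidate is pending at 25% to 50% of entries, prognosis is seen with correlation 0.5 to 1.0, nobody is passed over more than twice, and covariates carry 25% to 75% of the shift. A reader might take 0.25 SD as the expected bias. It needs v = 0.5, which reordering approaches only at the extreme: with a second candidate always pending and prognosis seen perfectly, the simulation gives v of 0.41, or 0.58 without the pass-over limit. The bias is smaller than the 0.44 SD half-width, but it is systematic and the confidence interval would not show it.

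The mismatch between 3.1 and 5.1 is a separate wording fault. It opens late exclusion, for which no size was derived.

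**What to change.** **Main change**, for envelopes 61 to 80 and any unused from 1 to 60. Amend 5.2 and 4.5 so that someone outside enrolment, for example the statistician already on the grant (7.2), prepares and holds the sequence, with a named deputy. Keep 10/10 for 61 to 80. Suggested text: *The RA does not prepare, hold or open allocations. Once consent is signed, eligibility is settled and the baseline is complete, the RA registers the participant. The holder records ID, date and time, then releases the next assignment in order of registration.*

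**If that is not workable**, require sealed, opaque, numbered envelopes, locked away from the RA and opened only after the completed baseline is logged, with envelope number and opening time recorded.

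**Separately**, reconcile 3.1 with 5.1. Either define the criteria that 3.1 refers to or remove the one-week allowance, so that eligibility is settled before allocation and nobody can be ruled out late.

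**Cost.** One call and a short wait per participant, longer if neither holder nor deputy can be reached. No new staff are needed, and sample size and analysis do not change. Two limits remain. The RA learns each arm afterwards, so counting past assignments stays possible. The holder knows the sequence, and since 7.5 lets the statistician analyse the data, the holder should ideally not be the analyst.

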### **5.3 Informing Participant of Treatment Assignment**

After the assessments and evaluations are complete, the participant should be informed of the treatment assignment and given an outline of his or her responsibilities, based on the specific treatment assignment. For MICRA, participants will be given the therapist’s name, session location, starting and ending dates and times. The participant will then attend the initial session(s). Participants randomized to SWNARC will be scheduled with [name] and they will need to follow through with SWNARC Intake/Assessment processes. Once they complete the SWNARC intake/assessment process they will be assigned a therapist.

After a participant has been randomized to treatment, the goal is to maintain a good research relationship, prevent attrition from the study, and maximize the collection of data in a complete and timely manner.

### **5.4 Tracking Systems**

Chapter 3 describes tracking systems used through the screening and recruitment phase. Participants will also be tracked in the Tracking Log and Participant Enrollment Log after they are randomized. The Tracking Log includes: 1) participant ID; 2) date; 3) time; 4) Activity; 5) Results; and 6) RA initials. All contact with participants should be documented in the Tracking Log. The Participant Enrollment Log includes: 1) name; 2) age and gender; 3) consent and baseline date; and 4) follow-up ideal and actual dates. Contact information for the participant on the Locator Form should also be updated on a regular basis (at research visits, and also at contacts in between these visits). A password-protected Linking Log will be kept on the RA's computer to link participant names and ID numbers, and also stored on the PI's private secure folder at CASAA, and these will be the only places where names and ID numbers are linked.

### **5.5 Taping Counseling Sessions**

MICRA and SWNARC sessions will be taped by the counselor and saved with only the participant's ID number, session date, and session number (e.g., 1001 9.22.11 S1). If participants wish to turn off the recording during the session, that is permissible. The consent form does include information on audio recordings, so that prior to study enrollment individuals are made aware of the taping process, and the taping process also is mentioned during the jail informational sessions.

Counselors will receive standardized training in MI and CRA as well as coaching calls until they reach criterion and to maintain fidelity. Adherence will be monitored by digital audio recordings of counseling sessions and supervision. These digital files are e-mailed using Meo encryption software and downloaded to Sendspace for the trainers, [name] and [name], who are both licensed professionals and who have completed CITI training. If therapy drift is observed, the counselors will be retrained.

Additionally, tapes will be encrypted using MEO Encryption software and saved on a flash drive and then transferred to a secure folder at CASAA using the VPN, a secure direct connection to CASAA. Only the PI, RA, and coders will have access to the folder. The tapes will be coded by an undergraduate or graduate student who works at UNM, or the tapes might be coded by the PI. The coding is not done to code any personal information. All tapes will be destroyed after coding has been completed.

## Chapter 6: Follow-up Research Assessments

### **6.1 Overview of Follow-up Assessments**

Follow-up research visits will occur 4, 8 and 12 months after the baseline interview (only 4 and 8 months for Phase I). The follow-up interview can be split over multiple days if necessary, but it must be completed within one week. If the baseline interview took place over multiple days, the follow-up date will be calculated based on the Form 90 completion date. Follow-ups consist of both RA-administered and self-report questionnaires. Follow-ups are essential to the study outcomes because they provide information about treatment response. When presenting study findings, high follow-up rates (at least 80%) help to solidify confidence in the findings. The follow-up process is not restricted to the actual research interview: it begins as soon as the baseline interview is completed and continues until all follow-up data has been collected. Participants should be reminded to call the RA if they are planning to move or have a new phone number or address.

At the follow-up interviews, the RA will remind the participant of her role: *to collect research data before, during and after treatment in order to see how well the treatment is working*. She will explain that research staff are separate from treatment staff, and that information obtained during follow-up assessments will not be shared with the counselors. The division of responsibilities between the counselors and Research Assistant during treatment is defined so that serious issues that arise with the participant are referred to the therapist. When the active treatment is over, however, the situation becomes more difficult. The participant who – most likely – has established a good rapport with the research staff may use follow-up contact as ample time and opportunity to raise personal issues. Moreover, at this phase of the study, the participant may confuse data collection activities with aftercare services. It is important for the Research Assistant to identify the risk of crossing boundaries and to present such cases to the Project Coordinator.

Research interviews will generally occur in the MICRA offices, but can also occur at SWNARC in a private office or at the detention center. In the event that the participant is unwilling or unable to meet the interviewer at the treatment setting, the interview may be conducted over the phone. Home visits may be made by the RA to reschedule missed appointments or deliver reminder letters, but interviews will not be conducted in participants' homes.

### **6.2 Tracking Procedures**

#### **6.2.1 Routine Tracking Procedures**

All participants will be sent a reminder letter one month before their scheduled follow-up date (see Appendix G for a sample letter). Letters should be designed with care to exclude information that would compromise the participant's confidentiality. If letters are returned to the MICRA offices because they could not be delivered, the RA will use contacts on the locator to find a correct mailing address for the participant or text message the individual. When research staff correspond with a participant or locator (i.e., phone, mail, etc.), this information should be recorded and entered into the Tracking

Log. This will allow staff to determine when the next contact should take place as well as types of contact that have been successful.

One week prior to the follow-up interview, the RA will call the participant to remind them about their interview, confirm attendance or reschedule as needed, and make sure that they have transportation to the interview. The RA will also call the participant one day before the interview to remind them about their appointment. If an answering machine is reached, it is a good idea to attempt calling again in order to speak with a person. If someone other than the participant answers record the person's name and relationship to the participant. This information helps determine the feasibility of leaving another message with the same person. It also helps getting convenient times to reach the participant or a change in her/her schedule.

The RA will continue to call or text message the participant until she is able to confirm the follow-up appointment. If the participant does not show up for the interview and cannot be contacted to reschedule, the RA will continue to call them until she is able to reschedule the follow-up. In cases where the RA cannot reach the participant by phone, the RA may visit the participant's house to try and locate the participant for the follow-up interview.

For those participants who cannot obtain transportation to the interview, the RA will call SWNARC to reserve a car so that she can pick up the participant at their house, bring them to the MICRA offices for the interview, and then return them to their house after the interview. When scheduling baseline or follow-up interviews, the RA will check with participants to see if they will need a ride to the MICRA offices.

To protect the confidentiality of participants when sending text messages, only the RA's first name and MICRA office number and a request for a return call or text will be included in the initial text message. If the RA receives a return text message, she will text back to confirm that it is indeed the participant. If it is the participant, the RA can proceed with scheduling the next follow-up appointment via text message. If the individual responding to the message is not the participant, then the RA will text message back asking the individual to pass along a message for the participant to call her back ("Please have him/her call [name] at xxx-xxxx"). The cell phone will be stored in a locked file cabinet in the MICRA offices along with the locators and consents, and all messages will be immediately deleted after they are received. Text message exchanges will be documented in the study tracking logs.

If the participant does not come in for their follow-up research interview by the scheduled date (e.g., 4 months past the baseline interview), the RA will continue to contact them until the participant can be reached and the research interview is completed. This may include home visits. These repeated contacts will be done in a respectful manner that recognizes the importance of the participant to the research study. If the participant tells the RA that they do not want to do the follow-up at this time, the RA will ask if they can contact the participant again in a few weeks, or at the next follow-up.

The RA will continue trying to reach the participant through the date of their next follow-up. If the RA did not reach the participant for the previous follow-up (e.g., 4 mos), but does finally reach the participant to complete an interview **2 weeks or less prior to the next follow-up** (e.g., right before the date of the 8 mo follow-up), then that interview will count as the second follow-up (e.g., the 8 mo follow-up). If the participant is reached for an interview **prior to the 2 week window before the next follow-up**, but, for example, it is a month or two after the previous scheduled follow-up, then that interview will still count as the previous follow-up, and the RA will contact the participant again for the next follow-up and complete it as usual, but with **at least one month** in between follow-up appointments.

If a research interview has been missed, at the next interview the Form 90 and the ASI should be completed regarding the period from the last completed interview. If the participant cannot be reached for the final follow-up interview, the RA will continue contacting the individual for 4 mos. after the scheduled follow-up date.

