### **4.3 RA-Administered Assessments (\* = used in Personal Feedback Report for MICRA)**

#### **4.3.1 Form 90 Interview\***

The Form-90 obtains primary outcome data through a detailed, comprehensive assessment of daily alcohol and drug use patterns in the past 90 days. The measure uses a modified calendar review method to assess daily alcohol and drug use patterns and BAC/number of standard drinks on the heaviest day of drinking.

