### **4.4 Self-Report Questionnaires (\* = used in Personal Feedback Report)**

#### **4.4.1 Inventory of Drug Use Consequences – 2R (Recent)\***

The Inventory of Drug Use Consequences (InDUC-2R) measures consequences in the previous four months from drinking alcohol or using drugs in five domains: physical, interpersonal, intrapersonal, impulse control, and social responsibility.

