#### **4.4.5 Risk Behavior Questionnaire\***

The Risk Behavior Questionnaire (RBQ) is a shortened version of the Risk Assessment Battery (Navaline et al., 1994) with added questions from the Sexual Behavior Interview (SBI; Calsyn et al., 2009). It will provide a behavioral measure of sexual practices in the past 4 months. It includes questions on the frequency of unprotected sex by partner type, the number of partners in the assessment period, and percentage of time sex occurred under the influence of substances.

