### **6.3 Follow-up Assessments**

Follow-up assessments are listed in Table 6.1. Phase I participants do not have a 12-month follow-up; because of this they will complete more questionnaires at the 8-month follow-up than the Phase II participants do. The procedures for the BAC and the oral fluid drug test are provided in Section 4.2. Descriptions of the assessments in Table 6.1 are given in Sections 4.3 and 4.4. Several questionnaires inquire about a different time period when given at follow-up than when given at baseline. These questionnaires include (period of interest at follow-up in parentheses):

Form-90 Interview (time since last research interview)

Addiction Severity Index (past 30 days and time since last research interview)

SCID (time since baseline interview)

Inventory of Drug Use Consequences-2R (time since last research interview)

\*\*Locator form from the baseline interview is pulled out and updated at each follow-up and whenever study staff has contact with the participant

All other questionnaires inquire about the same time period at each research interview.

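### An interview up to about day 229 still counts as the 4-month visit, so the 4-month outcomes cover unequal periods; percent days abstinent should be given a fixed window

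*Protocol*

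**What the plan says.** Section 6.1 places the Phase II follow-ups at 4, 8 and 12 months after baseline. Section 6.2.1 then says how a late interview is labelled. Within two weeks of the next follow-up date it becomes that next follow-up. Before that, where for instance "it is a month or two after the previous scheduled follow-up, then that interview will still count as the previous follow-up", it keeps the earlier label, and "the RA will contact the participant again for the next follow-up and complete it as usual", with at least one month between the two. The month or two is introduced as an example, and no other upper limit is given.

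Section 6.3 sets the follow-up recall periods: "Form-90 Interview (time since last research interview" and "Inventory of Drug Use Consequences-2R (time since last research interview". For a first follow-up, the last interview is baseline.

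The two instruments differ in kind. Section 4.3.1 describes the Form 90 as a "modified calendar review method to assess daily alcohol and drug use patterns", covering 90 days at baseline. Section 4.4.1 says only that the InDUC "measures consequences in the previous four months from drinking alcohol or using drugs", in five domains.

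Section 7.5 enters percent days abstinent (PDA) and the InDUC level into a two-group MANOVA at the 4-month follow-up, with baseline levels as covariates. Two other provisions matter for the remedy. After a missed interview, section 6.2.1 takes the Form 90 and the ASI back to the last completed interview. Section 5.4 logs the ideal and the actual follow-up dates.

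**The concern.** Read together, sections 6.2.1, 6.3 and 7.5 let one outcome label cover very different periods. An on-time participant contributes roughly the treatment period. A late one contributes the treatment period plus up to three and a half further months. If the effect of MICRA fades after treatment, late interviews dilute the 4-month difference. Aim 4 (section 1.1) exists to estimate effect sizes, so the quantity being estimated should be the same for everyone.

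The same rule affects the InDUC, where a score over a longer recall is set against a four-month baseline score. The difference is in what can be done afterwards. A daily calendar can be cut to any window. A score over one recall period probably cannot.

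**Working it through.** **Latest interview that counts as 4-month.** Inputs: follow-ups at 4 and 8 months (6.1) and the two-week boundary (6.2.1). Assumption: one month = 365.25/12 = 30.4375 days.

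- 4 months = 4 × 30.4375 = 121.75 days.
- Boundary = 8 × 30.4375 − 14 = 243.5 − 14 = 229.5 days = 7.54 months. With true calendar months, the last whole day that still counts is day 227 to 230.
- Ratio of longest to on-time recall = 229.5/121.75 = 1.89.
- In the protocol's own example (one or two months late) recall is 5 or 6 months.
- If the booking instruction in section 4.5 means that interviews are held two weeks early, recall starts at 121.75 − 14 = 107.75 days, about 3.5 months.

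**Share of the longest window that lies after treatment.** Treatment lasts 16 weeks = 112 days. Section 3.1 allows up to one week to randomise and two weeks to start, so treatment starting 2 to 3 weeks after baseline would end at day 126 to 133.

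- End at day 112: (229.5 − 112)/229.5 = 51%.
- End at day 126: 45%. End at day 133: 42%.

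**Dilution of the PDA effect.** Assumptions, none from the protocol: a true effect of 10 points during months 0-4; late interviews uniform on 4.5 to 7.54 months; the same proportion late in both arms.

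- If the effect is gone after month 4, an interview at t months shows 10 × 4/t. The mean of 4/t over the late range is 4 × ln(7.54/4.5)/(7.54 − 4.5) = 4 × 0.516/3.04 = 0.679, so late interviews show 6.79 points on average.
- If the effect is halved, they show 10 × (0.5 + 0.5 × 0.679) = 8.40.
- Observed effect = 10 − (proportion late) × (10 − late value):

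| Proportion late, both arms | Effect halved | Effect gone |
|---|---|---|
| 10% | 9.84 | 9.68 |
| 40% | 9.36 | 8.72 |

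If the effect persists unchanged, there is no dilution.

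**InDUC.** The protocol gives no scoring, so size can only be illustrated. If items are rated per unit time, longer recall inflates nothing. Under ever/never scoring with one constant rate, an item endorsed by 30% over four months reads 1 − 0.7^(t/121.75): 36% at day 152 and 49% at day 229.5. These are upper bounds, since rates that vary between people give less.

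A simulation assumed gamma-varying rates, 40 ever/never items, 32 per arm (80% of 40) and a t-test. Rejection under no effect was 5.0% with equal lateness, 5.2% with 20% against 30% late, and 7.2% with 10% against 40% late.

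**Would a constant four-month InDUC recall be better?** At day 229.5 it would cover days 107.75 to 229.5.

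- Share after treatment: (229.5 − 112)/121.75 = 97%, or 85% and 79% if treatment ends at day 126 or 133.
- Share of months 0-4 retained: 14/121.75 = 11%.
- In the same simulation, with the effect gone after month 4 and 25% late in both arms, a true 9.5-point difference reads 8.9 under the present rule and 8.2 under constant recall.

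**The case against.** The strongest reply is that the recall rule is deliberate and coherent. Recall since the last interview gives contiguous coverage for the over-time models in section 7.5 and always includes the whole of months 0-4. Sections 4.5 and 6.2.1 also work against lateness through early booking, a letter, two calls and transport. The 7.5-month case is the extreme. A baseline covariate need not share the outcome's window: the baseline Form 90 covers 90 days against about 120 at follow-up, and under randomisation a mismatch costs precision, not validity. All of this stands, and it keeps the point small. It does not give the 4-month PDA a uniform definition, which the calendar could supply at almost no cost.

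A reader might infer three stronger claims that the documents do not support.

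- **The arm comparison is biased.** That needs lateness to differ by arm, and the protocol gives no lateness rates. With equal lateness the false-positive rate stays at 5.0%.
- **The follow-up InDUC should be reset to four months.** There is a precedent. Of the Risk Behavior Questionnaire the protocol says "It will provide a behavioral measure of sexual practices in the past 4 months", and section 6.3 adds that "All other questionnaires inquire about the same time period at each research interview". But constant recall moves late scores almost wholly past treatment and dilutes a fading effect more. A persistent effect would favour it. The protocol does not say which applies.
- **The InDUC recall stretches to eight months after a missed 4-month visit.** This is unsettled. Section 6.3 would imply it, but the missed-interview rule in section 6.2.1 names only the Form 90 and the ASI.

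That late InDUC scores cannot be cut back is itself an inference, because section 4.4.1 describes neither item dating nor scoring.

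**Conclusion.** The point holds and is minor. The stated rules let the two key 4-month outcomes cover about 4 to 7.5 months, up to 1.89 times the on-time period, and nothing in the protocol truncates or rescales them. This rests on the text and date arithmetic alone.

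The consequence for PDA is a loss of about 0.2 to 1.3 points on a 10-point effect. That figure depends on assumed lateness of 10-40%, equal in both arms, and on an effect that is halved or gone after month 4. For the InDUC the definition is uneven, but the size of any distortion cannot be fixed from the protocol and may be nil.

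**What to change.** **PDA.** In section 7.5, define the Form 90-based primary PDA over one fixed window after the baseline Form 90, for example days 1-120.

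- Truncate late 4-month calendars to that window.
- Fill a missed 4-month visit from the 8-month Form 90, which section 6.2.1 already runs back to the last completed interview. If an interview is held at about day 108, the remaining days to 120 can come from the next Form 90 in the same way.
- Section 7.5 also derives PDA from the saliva tests. A saliva result from a late visit cannot be moved back to month 4, so the fixed window should be stated for the Form 90 measure.

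**InDUC.** Keep every score in the primary analysis. Report interview timing and recall length by arm from the dates logged under section 5.4. Add a sensitivity analysis restricted to interviews near month 4, for example days 108-152. With the late interviews assumed above, (7.54 − 5)/(7.54 − 4.5) = 84% of them fall outside that range. At 10-40% late this leaves out 8-33% of scores, about 3 to 11 of 32 per arm, so it should not be the primary analysis. A constant four-month recall remains an option if the team prefers to match the baseline window and accepts the trade-off shown above.

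**Cost.** Wording in section 7.5 and analysis programming, with no new visits, participants or data fields. The price is longer recall for PDA values recovered from later interviews.
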